9.7.1.2. Hypothesis for cohort analysis

Hypothesis (HA2): The incidence of new onset PMR and GCA in the RZV exposed cohort will differ from the incidence in the RZV unvaccinated comparator, as determined by a hazard ratio not equal to 1.

These hypotheses will be tested separately for each of the two primary HOIs during a 183-day risk period. With a cohort ratio of 1:4 RZV vaccinated to RZV unvaccinated comparator, a total sample size of 438 239 for PMR has 80% power to detect a relative risk of \geq 2.0 and a total sample size of 723 362 for GCA has 80% power to detect a relative relative risk of \geq 3.0.

9.7.1.3. Statistical analysis sequence

Since the sample sizes needed are HOI dependent, the statistical analysis will be staggered in phases. The proposed sequence is: gout; PMR and GBS; GCA, SVT, and ION as noted in Table 6. A comprehensive final report will be prepared upon completion of all primary and secondary analyses. This final comprehensive report will be submitted to the FDA Center for Biologics Evaluation and Research (CBER) and the EMA.

Outcome	Target risk to detect	Analysis Sequence
Gout	RR of ≥2	Phase 1
GBS	RR of ≥4	Phase 2
PMR	RR of ≥2	Phase 2
GCA	RR of ≥3	
SVT	N.a.	Phase 3
ION	N.a.	

Table 6 Sequence of analyses to be conducted

N.a.:Not Applicable

9.7.2. Handling of missing data

Based on the feasibility assessment study, we do not anticipate any missing data on age and sex. Approximately 0.01% of the population has missing information on the state of residence and 1.42% report "unknown" race. Individuals may be lost to follow-up if they lose eligibility or switch to Part C and all their data will be missing, at which point they will be censored in the analysis. Under the assumption that data are missing at random, multiple imputation will be used to impute missing values.

9.7.3. Participant disposition (Amended 15 July 2022)

Participant disposition will be summarized for the overall study population and for the RZV vaccinated and RZV unvaccinated comparators with a preventive health visit by computing:

- Number of individuals screened overall to determine eligibility for the study.
- Number and percent of individuals who do not satisfy criteria for inclusion in the study, overall and by cohort, for each of the following reasons:
 - Age < 65 at the index date
 - Not continuously enrolled in Medicare Parts A, B, and D for 365 days, *allowing* one calendar month gap, preceding the index date
 - Only enrolled in Medicare Part C
 - Qualify for Medicare due to a disabling condition
- Number of eligible *participants* in each cohort.

9.7.4. Descriptive analyses

Baseline characteristics of the RZV vaccinees and the RZV unvaccinated comparators will be compared using chi-square tests for categorical data and t-tests and simple linear regression for continuous data. According to the central limit theorem, with large sample sizes, as will be the case with the CMS CCW Medicare data, a two-sample t-test is robust to data that are not normally distributed. The Wilcoxon two-sample test is an alternative to the t-test because it makes no assumption about the underlying distribution of the data. It is best when the distribution of the two groups is similar, but it performs less optimally when the groups' distribution differs due to extreme outliers³⁰. Data will be inspected

using graphical plots to first test that statistical assumptions are met before implementing an approach.

- Comparisons on key baseline characteristics (i.e., before the index date) will include (see Section 9.3.4 for list of confounders):
 - Demographic characteristics: age at the index date, gender, race, ethnicity, region of residence, and the duration of Medicare Parts A, B, and D enrollment preceding cohort entry.
 - Medical comorbidities: common chronic conditions being considered that may confound the exposure-outcome association.
 - Health service use: number of all cause inpatient and ED visits, use of DME, hospice, home health, and SNF.
 - Preventive health services: Receipt of vaccine (age-recommended vaccine: influenza, pneumococcal, and tetanus, diphtheria, pertussis).
- Evaluation of the characteristics by patterns of RZV dosing will include:
 - Comparison of the baseline characteristics of individuals who receive only one dose with individuals who receive both doses of RZV.
 - Characterize RZV dosing patterns such as the mean and median time between Dose 1 and Dose 2.
 - The EMA wishes to see whether a meaningful number of study *participants* receive Dose 2 within 2 months after Dose 1 in order to determine the applicability of the study results to the European context. In accordance with this request, we will report the proportion of all 2-dose recipients receiving the second dose on days 28-60 after the first dose.
 - Report on the number of GBS cases with evidence in the inpatient or outpatient claims of respiratory or gastrointestinal infection (including COVID-19) in the 60 days prior to the GBS diagnosis, noting in which post-RZV windows (risk versus control) these GBS cases occurred.

9.7.5. Analysis population (*Amended 15 July 2022*)

Population for the SCRI design analyses

Only the cases of new-onset gout, GBS and SVT recorded in the RZV exposed cohort during either the risk or the control windows will be included in the respective HOI SCRI analysis.

Population for the cohort design analyses

The study population for the cohort design will comprise all RZV exposed and RZV unvaccinated comparators with a preventive care visit who satisfy the inclusion criteria. With the cohort design, to exclude prevalent cases of the HOI prior to the index date, all *participants* who had the HOI at any point in the 365-day pre-vaccination baseline period will be excluded.

Generating an index date for unexposed comparators. In an attempt to control healthy user bias among individuals who receive the RZV vaccine, the unvaccinated comparators will be selected from individuals who have at least one preventive care visit. The steps described below will be performed separately for Dose 1 and Dose 2.

- 1. Create a pool of eligible comparators with at least one preventive care visit.
 - The pool of eligible comparators are unvaccinated individuals who had at least one preventive care visit, which is defined as having at least one visit for a routine adult annual exam OR at least one preventive screening intervention performed (Table 2).
 - To ensure complete data for the baseline period preceding cohort follow-up, individuals must be continuously enrolled in Medicare Parts A, B, and D for a minimum of 365 days preceding the preventive care visit. *Continuous enrollment is determined by Medicare enrollment in the month of the preventative care visit and enrollment in at least 11 of the 12 preceding months.* Visits that do not satisfy this criterion will be excluded. For individuals with multiple preventive care visits, only visits that do not meet the eligibility criterion will be excluded. For individuals with only one preventive care visit, the entire person will be excluded if the visit does not meet eligibility criterion.
- 2. Randomly select one preventive care visit from eligible comparators. For an individual to be eligible as a comparator, the individual must not have had RZV at any time in available history prior to or on the day of the preventive care visit.
- 3. The preventive care visit is the index date for the unexposed comparator.

9.7.6. Inferential analyses for the primary outcomes (*Amended 15 July 2022*)

An overview of the planned primary, secondary, and sensitivity analyses were presented earlier in Table 1. Details of the analysis are described here.

- GBS and gout will be analyzed using a SCRI design
- PMR and GCA will be analyzed using a cohort design

Analysis of the SCRI Design

Additional inclusion requirements for the SCRI design analyses for new onset (i.e., incidence) primary HOIs GBS and gout include:

- 1. Receipt of RZV vaccination;
- 2. First occurrence in a 365-day look-back from the HOI in the risk or control interval;
- 3. Continuously enrolled in Medicare Parts A, B, and D fee-for-service for at least 365 days preceding the date of RZV vaccination. Continuous enrollment is determined by Medicare enrollment in the month of the RZV vaccination and enrollment in at least 11 of the 12 preceding months.
- 4. *Continuous* enrollment in Parts A and B (and in the case of gout Part D to capture gout-specific medication) through the end of the respective control interval.

The use of a first-in-365-days definition of HOI incidence is important and customary with the SCRI design to establish an equal opportunity for a case to be ascertained regardless of where in the follow-up (risk and control) period it might appear. The enrollment requirement for the defined amount of follow-up time, i.e., through the end of the control interval, will exclude people who die or lose eligibility before that time. However, because the HOIs addressed in this study are usually not fatal, we do not expect this requirement to produce any appreciable bias in our analyses. Moreover, the follow-up time (risk and control) is relatively short (84 and 60 days for GBS and gout, respectively), and we do not expect exclusion due to death would impact many individuals. In the relatively short follow-up time, we also do not anticipate loss of eligibility will produce appreciable bias in the analyses.

Per US schedule, RZV is indicated as a two-dose schedule, 2 to 6 months apart, thus it is not possible to define a consistent control interval for Dose 1. The control interval following Dose 1 may overlap with the risk interval following Dose 2. Therefore, the control interval following Dose 1 will depend upon the time between doses. The potential scenarios are illustrated in Figure 1.

- Shortened control window for both doses: This will yield a single risk estimate but will use a 3-week (days 43-63) control window for both doses. Dose 1 control window cases will be excluded if also in the Dose 2 risk window.
- Allow a 6-week control window for both doses: This will yield a single risk estimate and will use days 43-84 after Dose 1. The Dose 1 control window cases will be excluded if also in the Dose 2 risk window.

Sensitivity analyses for SCRI design

- Separate dose analysis for Dose 1 and Dose 2: This will yield separate risk estimates for Dose 1 and Dose 2. This risk and control windows for each dose will be defined according to the primary analysis.
- Subgroup analysis of dose compliant individuals who receive both doses according to the US schedule, i.e. within 2 to 6 months: The analysis will be similar to the primary combined dose analysis yielding one risk estimate, but in a subset of the vaccines who receive the vaccine as indicated.

Potential seasonality adjusted SCRI analyses for GBS and gout We will assess any seasonal pattern of RZV vaccination graphically, and will adjust for seasonality in secondary SCRI analyses for GBS and gout, as both of these outcomes are known to have a seasonal pattern.

Analysis of the Cohort Design

Additional inclusion requirements for the cohort design analyses for new onset (i.e., incidence) primary HOIs PMR and GCA include:

- 1. RZV vaccine exposed and a preventive care visit comparator;
- 2. A 365-day look-back from the index date (i.e., vaccination or preventive care visit date) to rule out prevalent cases;
- 3. At least 365 days (1 year) of Parts A, B, and D *continuous* enrollment prior to the index date. *Continuous enrollment is determined by Medicare enrollment in the month of the RZV vaccination or preventative care visit and enrollment in at least 11 of the 12 preceding months.*

Primary analysis of separate doses.

The analysis accounts for the variation in the interval between Dose 1 and Dose 2. The risk period after Dose 1 may overlap in part with the risk period after Dose 2 and/or the baseline period before Dose 2. To mitigate time-window bias, there is similar risk period after each dose.

The primary analysis will assess each dose separately and will yield two separate risk estimates for Dose 1 and Dose 2. Exposure is defined as at least one dose of the RZV vaccine. The risk period for the cohort analysis is 183 days from index date. The index dates are Doses 1 and 2 is the vaccination date for the RZV cohort and preventive care visit date for the RZV unvaccinated cohort. The scenarios for the primary analysis are illustrated in Figure 2.

Figure 2 Cohort Design: Primary analysis with separate Dose 1 and Dose 2 analysis

Secondary analyses of the cohort design.

The secondary analyses will combine Dose 1 and Dose 2.

- One risk estimate: This secondary analysis of combined doses does not distinguish between doses to yield one risk estimate.
- Two separate risk estimates: An additional secondary analysis combines Dose 1 and Dose 2 in the same analytic model but yields two separate risk estimates.

All individuals will be followed up for 183 days from the Dose 1. The maximum allowable spacing between doses will be 365 days. This means that Dose 2 is not included in the analysis if it is received more than 365 days after Dose 1. We anticipate the majority of individuals will receive Dose 2 within 365 days. RZV vaccinated individuals may have up to two measures (i.e., one for Dose 1 and one for Dose 2). The RZV unvaccinated comparators similarly will have up to two measures for the index dates for preventive care visits. Robust variance estimators will be used to account for repeated measures on the same individual.

Sensitivity analysis of the cohort design.

• Dose compliant analysis: The sensitivity analysis is restricted to the sub-sample that received Dose 1 and Dose 2 per US dosing schedule, i.e., 2-6 months apart. Analysis will be conducted similar to the secondary analysis (i.e combined doses yielding a single risk estimate and separate doses yielding two risk estimates).

Sensitivity analysis of alternative definition of GCA

• The number of cases and the incidence rate (or cumulative incidence) among vaccinated and preventative care comparators who are identifed using the sensitivity analysis HOI definition of GCA (Table 3 Column 10) will be reported. Futher analysis consistent with the primary (1°) analysis for the cohort design (i.e. analysis of separate doses) will be conducted, if an appropriate number of cases are identified to allow meaningful inference.

Censoring events. Exposed person-time will be defined as the period between the index date and the earliest of the following events:

- End of study period (defined as the lesser of 183 days after the index date or Dec 31. 2021)
- Date of disenrollment from Medicare Parts A, B, and D
- Date of death
- Date of *Shingrix* vaccination among comparators
- Date of *Zostavax* vaccination
- Date of first diagnosis of the outcome of interest.

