8.1. Primary objectives

- 1. To assess the risk of new onset GBS within 42 days following RZV vaccination using a SCRI design.
- 2. To assess the risk of new onset gout within 30 days following RZV vaccination using a SCRI design.
- 3. To assess the risk of new onset PMR within 183 days following RZV vaccination using a cohort design.
- 4. To assess the risk of new onset GCA within 183 days following RZV vaccination using a cohort design.

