Combined analysis of Dose 1 and Dose 2 yielding separate risk estimates. To generate a separate risk estimate for each dose in a combined analysis, where a binary indicator defines the Dose 1 and Dose 2 risk windows, a time-varying Cox proportional hazards regression models will be used. In the time-dependent model, we allow the risk window to vary for each dose. The time after dose 1 until dose 2 or end of follow-up if no dose 2 occurs defines the dose 1 risk window, and the time from dose 2 until end of follow-up defines the dose 2 risk window. Thus, a *participant* who receives two doses will contribute time to the dose 1 risk window and the dose 2 risk window. In the unvaccinated comparators the time from index date to end of follow-up is considered unexposed time. A general form of time-dependent Cox models can be written as:

 $h_i(t,x) = \lambda_0(t) \exp[\beta_1 x_{i1} + \dots \beta_2 x_{i2}(t)]$

where x_{i1} represents a time-independent variable, and x_{i2} represents the time-dependent variable. This analysis will use the full cohort and obtain estimates for both doses

whereas the primary separate dose analysis either ignores dose 2 or includes only the subset of the sample who received 2 doses.

This analysis allows us to use the full cohort to compare the findings to the primary separate dose analysis. The primary Dose 1 analysis ignores Dose 2, and as such the events after Dose 2 may be attributed to Dose 1, thereby increasing the HR for Dose 1 (and its unknown which dose carries the highest risk). The primary Dose 2 analysis only includes individuals who did not experience the event after Dose 1, which could reflect potentially the more robust individuals. This could bias the estimate towards the null, and it is difficult to determine whether the estimate is a function of the vaccine or the characteristics of the Dose 2 subgroup. The time-varying model for this analysis uses the entire cohort, and attributes events to the respective dose risk window yielding a HR for each dose. Therefore, the full cohort sensitivity analysis allows us to estimate the hazard for each individual dose risk and to compare the results with the primary analysis estimates.

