The effect estimates generated from the time-dependent Cox proportional hazards model will be a hazard ratio for Dose 1 relative to unexposed and a hazard ratio for Dose 2 relative to unexposed. Both hazards are generated in the same model with the full cohort, using time since the Dose 1 index date or the preventive care visit.

Sensitivity analysis for receipt of the Dose 1 and Dose 2 on schedule. The sensitivity analysis will be restricted to the sub-sample of individuals who receive both RZV doses on schedule per US label. This will test the sensitivity of the primary and secondary analyses, which examine the HOI incidence regardless of the dose spacing. This will follow the primary separate dose analysis and the secondary combined dose analysis.

Supplemental analysis

Some individuals in the analysis may contribute person-time both to the comparison group and (subsequently) to the RZV-vaccinated group. At CBER's request, a supplemental analysis will be conducted for the primary analysis, excluding from the control arm those *participants* who received RZV at any point, so that each *participant* contributes person-time to only one arm.

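### In the secondary two-hazard-ratio cohort model, follow-up ends 183 days after Dose 1, so the Dose 2 window shrinks with dose spacing and is empty for Dose 2 on days 183-365, which the plan says it includes

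*Combined protocol and SAP*

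**What the plan says.** Section 8.1 sets a 183-day horizon after vaccination, for example "To assess the risk of new onset PMR within 183 days following RZV vaccination using a cohort design"; Table 1 gives days 1-183 for PMR and GCA. For the primary separate-dose analysis, Section 9.7.6 treats each dose as an index date and states "The risk period for the cohort analysis is 183 days from index date".

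The paragraph on secondary combined-dose analyses in Section 9.7.6 reads differently. It says "All individuals will be followed up for 183 days from the Dose 1", followed by "The maximum allowable spacing between doses will be 365 days" and "This means that Dose 2 is not included in the analysis if it is received more than 365 days after Dose 1". The censoring list in the same section ends follow-up at the earlier of 183 days after the index date and 31 December 2021.

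Section 9.7.9 describes the secondary model that yields two HRs. Dose 1 time ends at Dose 2, and "the time from dose 2 until end of follow-up defines the dose 2 risk window". Comparators are unexposed from their index date to the end of follow-up. Both HRs come from one model "using time since the Dose 1 index date or the preventive care visit". The dose-compliant sensitivity analysis (both doses 2-6 months apart) repeats this model. The one-HR partly conditional model is different: Section 9.7.9 runs it on time since each dose.

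**The concern.** A Dose 2 counted up to day 365 cannot have a 183-day risk window if everyone stops at day 183 after Dose 1. In the two-HR model, the amount of Dose 2 time then depends on when Dose 2 was given. Early recipients supply most of it, and later post-Dose 2 days are seen only in people with short spacing.

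Section 9.7.9 presents this model as a check on two weaknesses it admits in the primary analyses: the Dose 1 analysis may absorb events that follow Dose 2, and the Dose 2 analysis rests on a selected subgroup. It intends to compare the model's results with the primary estimates. For Dose 2 that comparison would set a truncated, spacing-dependent window against a full 183-day one. If the two Dose 2 HRs differed, the reader could not tell whether the cause was selection into the primary Dose 2 analysis or the shorter window.

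**Working it through.** **The plan's own figure.** Table 5 assumes six months of follow-up per person. With exposed share p = 0.2, two-sided alpha 0.05, 80% power and T = 0.5 year, the Poisson-regression formula is

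N = [1.960·√(1/(p(1-p))) + 0.842·√(1/(1-p) + 1/(p·RR))]² / [(ln RR)² · baseline · T].

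- PMR, RR 2, baseline 0.000405: N = 438,239, as stated.
- GCA, RR 3, baseline 0.000092: N = 723,362, as stated.

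All nine rows reproduce. Table 5 is sound for a full six-month window, but that window does not describe Dose 2 time in the two-HR model.

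**Dose 2 time in the two-HR model.** Inputs: follow-up ends on day 183 after Dose 1 (9.7.6); Dose 2 is kept to day 365 (9.7.6); Dose 2 time runs from Dose 2 to the end of follow-up on the Dose 1 clock (9.7.9). With s the day of Dose 2:

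- Dose 2 days seen = max(0, 183 - s)
- follow-up needed for a full window = s + 183

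| s | Dose 2 days seen | Share of 183 | Follow-up needed (day) |
|---|---|---|---|
| 60 | 123 | 67% | 243 |
| 84 | 99 | 54% | 267 |
| 90 | 93 | 51% | 273 |
| 120 | 63 | 34% | 303 |
| 150 | 33 | 18% | 333 |
| 180 | 3 | 2% | 363 |
| 183 | 0 | 0% | 366 |
| 365 | 0 | 0% | 548 |

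Taking two months as day 60 gives the upper bound of 123 for on-schedule doses. Section 9.7.6 places days 43-60 before the two-month point, so day 61 and 122 days may be the stricter figure. An early, off-schedule dose sees more: 155 days at s = 28.

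**Average loss.** The documents give no full spacing distribution, so these are assumptions:

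- Uniform spacing over days 60-183: mean 61.5 days (34%).
- Half on days 60-84 and half on days 85-183: (111 + 49)/2 = 80 days (44%). This split follows Section 9.5.2, which expects Dose 2 to cut into the Dose 1 control window in about 50% of two-dose recipients.

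**Does a per-dose reading of the censoring rule help?** Suppose vaccinees were followed for 183 days from Dose 2. The model clock still starts at Dose 1 or at the preventive visit, and comparators are still capped at 183 days from their visit. After day 183 on that clock no unexposed person is at risk, so later events give no direct Dose 2 versus unexposed comparison. Section 9.7.6 allows comparators up to two index visits, but with time measured from the visit nothing in the text places a second visit beyond day 183 of the clock.

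**Data available.** Claims run to December 2021. The longest case needs 365 + 183 = 548 days, and 31 December 2021 minus 548 days is 1 July 2020. For s = 183, 366 days are needed, which is available for Dose 1 dates up to 30 December 2020.

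**The case against.** The strongest defence is that the plan intends a per-dose clock. Section 9.7.6 makes both doses index dates, gives vaccinees up to two measures, accepts Dose 2 to day 365, and censors at 183 days after the index date. The 365-day rule makes little sense otherwise. As evidence of intent this has force, and it settles the one-HR model, which already runs on time since dose. It does not rescue the two-HR model, for the reason shown in the working: its comparators leave by day 183 on the same clock.

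A second defence stands. For checking the primary Dose 1 HR, 183 days from Dose 1 is the right window: the same span and clock, with events split at Dose 2. Only the Dose 2 comparison suffers.

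A reader might infer more than the documents support:

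- That the primary objectives are compromised. They are not, because the primary Dose 2 analysis has its own 183 days.
- That the 183-day period was chosen to catch late-onset PMR or GCA, so that truncation defeats its purpose. No section says so. Section 9.1 mentions the long period and insidious onset only to explain why a self-controlled design was rejected.
- That most Dose 2 time is lost. The size depends on spacing: the half of two-dose recipients suggested by Section 9.5.2 would keep at least 99 days each. The documents give no share for doses after day 183, and these are largely off schedule.

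**Conclusion.** The point holds for the secondary two-HR time-varying Cox model and its dose-compliant version, and for nothing wider. As written, Dose 2 time is max(0, 183 - s): at most about 123 days (67%) on schedule, at least 99 (54%) for doses by day 84, and zero for doses on days 183-365 that the plan says it includes. The resulting Dose 2 HR is not comparable with the primary one. The per-person figures need only the stated rules and two months taken as 60 days; the averages of 34% and 44% rest on assumed spacing. Because the affected analysis is secondary, this should be corrected before analysis but does not threaten the primary conclusions.

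**What to change.** Reconcile the secondary-analysis paragraph and the censoring list in Section 9.7.6 with the two-HR model in Section 9.7.9:

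- Give each counted dose its own risk window of up to 183 days, with Dose 1 time ending at Dose 2.
- Remove vaccinee time outside a dose window from the risk sets; do not return it to the reference group.
- Follow comparators over the same span of the Dose 1 clock, still censored at RZV, so that unexposed people remain at risk.
- State that the sentence fixing 183 days from Dose 1 does not govern the one-HR partly conditional model.
- Keep the version that stops 183 days after Dose 1 as the matched check on the primary Dose 1 HR.

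If truncation is intended, drop the 365-day inclusion rule for this model and state that its Dose 2 HR is not comparable with the primary Dose 2 HR.

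The cost is revised wording and somewhat more code; no further data years are needed. Comparators would be followed longer on covariates measured before their index date. Censoring at 31 December 2021 would shorten some windows: at the maximum 365-day spacing it affects Dose 1 dates after 1 July 2020. The COVID-19 sensitivity analysis in Section 9.7.8 is aligned with the primary analyses, so it need not change.

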7. RATIONALE AND BACKGROUND

Herpes zoster (HZ), the result of reactivation of latent varicella zoster virus (VZV) in dorsal root ganglia, most commonly presents as a painful vesicular dermatomal rash. However, complications such as post-herpetic neuralgia (PHN), as well as disseminated disease in the immunocompromised population, can lead to significant disability and morbidity¹. There are an estimated one million cases of HZ in the United States (US) annually, resulting in \$5 billion in healthcare expenditures per year². Risk factors for HZ include older age and immunocompromising conditions^{3,4}.

Shingrix, recombinant zoster vaccine (RZV), is a subunit, adjuvanted VZV vaccine. It is approved for the prevention of HZ in adults \geq 50 years of age in several countries within Europe and the US. Shingrix is a two-dose vaccine, in Europe, Doses 1 and 2 should be given 2 months apart, with the possibility of extending the timing of Dose 2 to 6 months. In the US, RZV is given 2 to 6 months apart. Since this study is being conducted in the US, the recommended dosing schedule in the US will be considered. The Advisory Committee on Immunization Practices recommendations for RZV include the following: 1) RZV (as two doses 2 to 6 months apart) is recommended for immunocompetent adults aged 50 years and older; 2) RZV is recommended for immunocompetent adults previously vaccinated with the zoster vaccine live (ZVL, *Zostavax*); and 3) RZV is preferred over ZVL⁵. Vaccine efficacy against HZ in the two pivotal Phase III studies was 97.2% in adults \geq 50 years of age (ZOE-50)⁶ and 91.5% in adults \geq 70 years of age⁷. Pooled safety analyses of clinical data from these two Phase III studies included a total of 14 645 RZV and 14 660 placebo recipients, with a median follow-up duration of 4.4 years⁸. The pooled analysis demonstrated a comparable incidence of unsolicited adverse

events (AE) in the Day 7 through Day 29 follow-up period (excluding Day 0 through Day 6 where reactogenicity was observed to be higher in RZV versus placebo recipients). Serious adverse events (SAE), and potential immune-mediated disorders (pIMDs) between the RZV and placebo groups, and specific SAEs and pIMDs were within the expected incidence for the study age group⁸.

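### The cohort dose-compliant analysis counts Dose 1 follow-up only in people who later received Dose 2 on schedule, so its Dose 1 hazard ratio is biased downward if an event between doses makes that Dose 2 less likely

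*Combined protocol and SAP*

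**What the plan says.** **Who enters.** Table 1 and section 9.7.6 define a cohort sensitivity analysis "restricted to the sub-sample that received Dose 1 and Dose 2 per US dosing schedule", that is, two to six months apart. Section 9.7.9 repeats it: "The sensitivity analysis will be restricted to the sub-sample of individuals who receive both RZV doses on schedule per US label". Section 9.7.7 has ION analysed in the same way as PMR and GCA.

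**When time starts.** Section 9.7.6 states: "All individuals will be followed up for 183 days from the Dose 1". In the model with two estimates (9.7.9), "The time after dose 1 until dose 2 or end of follow-up if no dose 2 occurs defines the dose 1 risk window", and both hazard ratios are obtained "using time since the Dose 1 index date or the preventive care visit". Comparators contribute unexposed time from their index date to the end of follow-up, with no requirement to reach any later qualifying event.

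**What is reported.** Section 9.7.6 asks for one combined estimate and two dose-specific estimates in the on-schedule subset. Table 1 and 9.7.6 tie this to the secondary combined analyses. Section 9.7.9 is wider: "This will follow the primary separate dose analysis and the secondary combined dose analysis".

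**What is acknowledged.** Sections 9.7.9 and 9.9 recognise selection into the Dose 2 analysis and a possible underestimate there. Neither mentions Dose 1 time that is counted only if a Dose 2 follows.

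**SCRI counterpart.** Section 9.7.6 also plans a "Subgroup analysis of dose compliant individuals who receive both doses according to the US schedule", which yields one combined estimate.

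**The concern.** In the on-schedule subset, all of the Dose 1 window lies before the event that decides membership. A vaccinee who develops PMR, GCA or ION between doses is kept only if Dose 2 still arrives within the schedule. A comparator with the same event is always kept. This is conditioning on the future in one arm, and it removes exposed events but no comparator events.

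The documents make some deterrence plausible. A PMR or GCA case needs two oral glucocorticoid prescriptions (Table 3). Section 7 reports that the vaccine is "recommended for immunocompetent adults aged 50 years and older" who are immunocompetent, and section 9.3.4 lists autoimmune or inflammatory conditions and immunosuppressive regimens among the immunocompromised conditions.

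Section 9.1 presents this as the analysis of risk when Dose 2 follows the US schedule, and 9.7.9 uses it to test the primary and secondary results. A check that leans towards lower risk could appear to confirm safety, or to contradict a true Dose 1 signal.

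**Working it through.** **1. Reading the plan's baseline rate.** Table 5 gives 438,239 for PMR (RR 2, 80% power, two-sided alpha 0.05, 1:4, baseline 0.000405). The Poisson-regression formula with exposed share p = 0.2 is

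N = [1.960·√(1/(p(1−p))) + 0.8416·√(1/(1−p) + 1/(p·RR))]² / (T · rate · (ln RR)²)

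The numerator is (1.960 × 2.5 + 0.8416 × 1.9365)² = 42.64. With T = 0.5 year, N = 42.64 / (0.5 × 0.000405 × 0.4805) = 438,239, which matches. With T = 1 it gives 219,119, which does not. So 0.000405 is a yearly rate, not a 183-day risk.

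**2. Dose 1 HR in the two-estimate model.** Let q be the proportional fall in on-schedule Dose 2 receipt after an event between doses. The documents give no value, so q is an assumption. Each Dose 1-window event is kept with relative probability (1 − q). Events are rare, so person-time hardly changes, and observed HR ≈ true HR × (1 − q).

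**3. Single combined HR.** Section 9.5.2 expects Dose 2 to cut short the Dose 1 control window, which ends at day 84, in about half of two-dose recipients. Assume half of second doses are uniform over days 60–84 and half over days 84–183. The mean is 0.5 × 72 + 0.5 × 133.5 = 102.75 days, or 0.561 of 183. With a 183-day record per dose and constant hazard, combined HR ≈ true HR × (1 − 0.561q/2).

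| q (assumed) | Dose 1 HR, true 1 | Dose 1 HR, true 2 | Combined HR, true 1 | Combined HR, true 2 |
|---|---|---|---|---|
| 0 | 1.00 | 2.00 | 1.00 | 2.00 |
| 0.10 | 0.90 | 1.80 | 0.97 | 1.94 |
| 0.25 | 0.75 | 1.50 | 0.93 | 1.86 |
| 0.50 | 0.50 | 1.00 | 0.86 | 1.72 |

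A simulation with 4 million vaccinees per scenario agreed: for a true HR of 2, the on-schedule subset gave 1.50 at q = 0.25 and 1.01 at q = 0.50. Using all Dose 1 recipients, with time ended at Dose 2 or day 183, it returned about 1.0 and 2.0 for every q.

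**4. Delay instead of cancellation.** If every event pushes Dose 2 to at least 60, 90 or 120 days after the event, a true HR of 2 becomes 1.83, 1.61 or 1.24.

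**5. Precision.** Take section 9.2.2's projection of about 2 million exposed and 8 million comparators, with q = 0 unless stated.
- PMR, 183 days: 405 and 1,620 events; SE of log HR = √(1/405 + 1/1,620) = 0.056.
- PMR, 84-day Dose 1 window, q = 0.25: 2,000,000 × 0.000405 × 84/365.25 × 0.75 = 140 exposed events and 745 comparator events; SE = 0.092. A null HR seen as 0.75 gives z = −0.288/0.092 = −3.1.
- PMR, same window, q = 0.10: 168 and 745 events; SE = 0.085. A null HR seen as 0.90 gives z = −0.105/0.085 = −1.2.
- GCA (yearly rate 0.000092), same window, q = 0.25: 32 and 169 events; SE = 0.19; z = −1.5.

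The on-schedule subset is smaller than 2 million, so the true SEs are larger.

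**6. SCRI subgroup, GBS windows, true IRR 2.** If risk-window and control-window events deter Dose 2 equally, the combined IRR stays 2.0. If control-window events deter more (50% against 25%), it rises to 2.31. In the reverse case it falls to 1.73.

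**The case against.** The strongest reply is that q is unknown and could be small. Table 3 allows the first glucocorticoid dispensing up to 6 months from diagnosis and the second up to 6 months after that, so steroid use need not precede Dose 2. The primary ION definition requires no steroid at all. A delay removes an event only if it carries Dose 2 past six months, and a delay that moves a Dose 2 from under two months into the schedule would add one. All of this stands: the size is uncertain, and the bias vanishes at q = 0.

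It is also fair that this is only a sensitivity analysis. The primary Dose 1 analysis and the full-cohort time-varying model do not require a later Dose 2, and section 9.7.4 compares one-dose with two-dose recipients. That limits the harm but does not repair the check.

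A reader might infer three stronger things that the documents do not support:
- **That the SCRI dose-compliant result is also biased low.** Both Dose 1 windows that are counted precede Dose 2, and no Dose 1 estimate is produced. Selection gives Dose 1 cases less weight, but the IRR can stay the same, rise or fall.
- **That the analysis will give HRs below 1 when there is no effect.** That requires q above 0.
- **That any such shift would be statistically significant.** That fails for small q, and for GCA even at q = 0.25.

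**Conclusion.** The point holds for the cohort dose-compliant analysis of PMR, GCA and ION. Its Dose 1 HR is multiplied by about (1 − q), so a true HR of 2 is seen as about 1.8, 1.5 or 1.0 at q = 0.10, 0.25 or 0.50. The combined HR is pulled down less, to about 1.94, 1.86 or 1.72. These figures rest on an assumed q, rare events and, for the combined HR, the assumed spread of Dose 2 dates.

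One gap could make matters worse. Person-time ends at first diagnosis (9.7.6, censoring events), and the text does not say whether someone diagnosed between doses who still receives Dose 2 on time belongs to the subset. If such people are dropped, q is effectively 1 and no Dose 1-window event remains.

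The primary results are not affected. The analysis should be changed because it serves as a check on them and, for any q above 0, errs in the reassuring direction.

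**What to change.** - In the on-schedule cohort subset, start follow-up at Dose 2, when on-schedule status is known. Use the comparators already selected for the Dose 2 analysis (9.7.5) and report only the post-Dose 2 HR. People diagnosed between doses then fall out as prevalent cases under the existing baseline rule.
- Drop the Dose 1 and combined HRs from that subset.
- Take any Dose 1 estimate from all Dose 1 recipients, ending Dose 1 time at any Dose 2 or day 183, without requiring a later Dose 2. The full-cohort time-varying model already defines its Dose 1 window this way. Ending time only at an off-schedule Dose 2 would not do, because events after an on-schedule Dose 2 would be credited to Dose 1, the misattribution that 9.7.9 itself describes.
- For the SCRI dose-compliant subgroup, state the selection on a later Dose 2 as a limitation, with no direction claimed.
- Reconcile 9.7.9 (follows the primary and secondary analyses) with Table 1 and 9.7.6 (secondary analyses only).

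The cost is revised wording and a simpler run of models already planned, with no new data. The plan loses an on-schedule Dose 1 estimate, which the current design cannot give validly. Selection into Dose 2 remains, as section 9.9 already acknowledges.
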